4.2.1 Primary Safety Endpoint

- Age 18-80: The overall mean change in HbA1c from baseline to end of 3-month study period. The goal is to show non-inferiority with a margin of 0.4% comparing to a threshold of -0.5% in reducing HbA1c from baseline to end of 3-month study period.
- Age 7-17: The overall mean change in HbA1c from baseline to end of 3-month study period. The goal is to show non-inferiority with a margin of 0.4% comparing to a threshold of -0.38% in reducing HbA1c from baseline to end of 3-month study period.

4.2.2 **Primary Effectiveness Endpoint**

- Age 18-80: The mean % of time in range (TIR 70-180 mg/dL [3.9 -10.0 mmol/L]) will be estimated and compared to a threshold of 73.7% by a non-inferiority test with a margin of 7.5% and a significance level of 0.025 (one-sided).
- Age 7-17: The mean % of time in range (TIR 70-180 mg/dL [3.9 -10.0 mmol/L]) will be estimated and compared to a threshold of 65.3% by a non-inferiority test with a margin of 7.5% and a significance level of 0.025 (one-sided).

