14.5.2 Analysis of Effectiveness Endpoint

14.5.2.1 Primary Effectiveness Endpoint

Age 18-80:

• The mean % of time, μ_{780G} , in range (TIR 70-180 mg/dL [3.9 -10.0 mmol/L]) will be estimated and compared by a non-inferiority test to the threshold of 73.7% with a margin of 7.5%. A significance level of 0.025 (one-sided) will be used. The 7.5%, which is approximately 100 minutes increase in TIR per day, was also observed from the HCL pivotal trials. It is loosely correlated to ~0.5% reduction in A1c as well. Analysis will be performed on the ITT and PP populations.

The hypothesis of non-inferiority is mathematically expressed as:

H₀: $\mu_{780G} \le 73.7\% - 7.5\%$

H_a: $\mu_{780G} > 73.7\% - 7.5\%$

Age 7-17:

 The mean % of time, μ_{780G}, in range (TIR 70-180 mg/dL [3.9 -10.0 mmol/L]) will be estimated and compared by a non-inferiority test to the threshold of 65.3% with a margin of 7.5%. A significance level of 0.025 (one-sided) will be used. The 7.5%, which is approximately 100 minutes increase in TIR per day, was also observed from the HCL pivotal trials. It is loosely correlated to ~0.5% reduction in A1c as well. Analysis will be performed on the ITT and PP populations.

The hypothesis of non-inferiority is mathematically expressed as:

H₀: $\mu_{780G} \le 65.3\% - 7.5\%$

Ha: $\mu_{780G} > 65.3\% - 7.5\%$

CIP336 Clinical Investigation Plan			
D00459338	Version E	Page 121 of 159	Mecttronic

Pass/Fail Criteria:

The study pass/fail criteria is based on statistical hypothesis of the primary endpoints. The study for each age cohort (age 18-80 and age 7-17) will be considered as success when the evaluation criteria of both primary safety and effective endpoints meets the predefined threshold per cohort.

Justification for Exclusion of Particular Information from the testing of the Hypothesis: Not Applicable.

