7.2 General Methodology

Summary statistics for continuous variables will be represented by number of subjects(n), mean, median, standard deviation and categorical variables will be represented by counts and percentages. P-values for hypothesis testing will be evaluated based on one-sided testing using significance level of 0.025. Confidence intervals if needed will be reported as two-sided 95% confidence intervals. For primary safety, primary effectiveness and secondary effectiveness endpoints, normality will be verified for appropriate statistical methodology. Comparisons between the outcomes in study period and the threshold will be performed using one sample T-test for testing the statistical significance of the difference if normality assumption is met or Wilcoxon signed rank test if normality assumption is not met. In addition, the mean, median, min, and max will be presented when the normality assumption is not met.

The templates for Tables, Listings and Figures (TLFs) will be available in the TLFs document.

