7.5.1 Age 18-80

For the following endpoints from age 18-80, the procedure test hierarchically the ordered hypotheses in sequence at level $\alpha = 0.025$ until a first hypothesis is non-rejected.

Primary Safety Endpoint

 Age 18-80: The overall mean change in HbA1c from baseline to end of 3-month study period. The goal is to show non-inferiority with a margin of 0.4%⁴ comparing to a threshold of -0.5% in reducing HbA1c from baseline to end of 3-month study period.

17-JUN-2024 Revision 4.0 Page 17 of 25

Primary Effectiveness Endpoint

Age 18-80: The mean % of time in range (TIR 70-180 mg/dL [3.9 -10.0 mmol/L]) will be estimated and compared to a threshold of 73.7% by a non-inferiority test with a margin of 7.5%^{5,6} and a significance level of 0.025 (one-sided).

Secondary Effectiveness Endpoints

- Age 18-80: The mean % of time in hypoglycemia (< 54 mg/dL [3.0 mmol/L]) will be estimated and compared to a threshold of 0.86% by a non-inferiority test with a margin of 2%⁷ and a significance level of 0.025 (one-sided).
- Age 18-80: The mean % of time in range (TIR 70-180 mg/dL [3.9 -10.0 mmol/L]) will be estimated and compared to a threshold of 73.7% by a simple superiority test and a significance level of 0.025 (one-sided).

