7.9.1 Pass/Fail Criteria

- The goal of the study for each age cohort (age 18-80 and age 7-17) is to evaluate both primary safety and primary/secondary effective endpoints according to the predefined threshold per cohort. Once all effective endpoints are met, the claim of superiority will be made.
- The goal of study for each age cohort (age 18-80 and age 7-17) will be also considered met when the evaluation criteria of both primary safety and effective endpoints meets the predefined threshold per cohort. However, the claim of non-inferiority will not be made.

Justification for Exclusion of Particular Information from the testing of the Hypothesis: Not Applicable.

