7.9.2 Primary Safety Endpoint

Age 18-80:

[figure not shown]
The overall mean change in HbA1c, $\Delta\mu_{780G}$, from baseline to end of 3-month study period will be estimated and compared by a non-inferiority test to the threshold of -0.50% with a margin of 0.4%⁴. A significance level of 0.025 (one-sided) will be used. Analysis will be performed on the ITT and PP populations.

The hypothesis of non-inferiority is mathematically expressed as:

 H_0 : $\Delta \mu_{780G} \ge -0.50\% + 0.4\%$

 H_a : $\Delta \mu_{780G} < -0.50\% + 0.4\%$

17-JUN-2024 Revision 4.0 Page 19 of 25

The null hypothesis will be tested against the alternative hypothesis using one sample t test if normality assumption is met, Wilcoxon signed rank test if normality assumption is rejected. Non inferiority of MiniMed 780G system utilizing insulin Fiasp (insulin aspart injection) for age 18-80 will be concluded if null hypothesis is rejected.

Age 7-17:

The overall mean change in HbA1c, $\Delta \mu_{780G}$, from baseline to end of 3-month study period will be estimated and compared by a non-inferiority test to the threshold of -0.38% with a margin of 0.4%⁴. A significance level of 0.025 (one-sided) will be used. Analysis will be performed on the ITT and PP populations.

The hypothesis of non-inferiority is mathematically expressed as:

$$H_0$$
: $\Delta \mu_{780G} \ge -0.38\% + 0.4\%$

$$H_a$$
: $\Delta \mu_{780G} < -0.38\% + 0.4\%$

The null hypothesis will be tested against the alternative hypothesis using one sample t test if normality assumption is met, Wilcoxon signed rank test if normality assumption is rejected. Non inferiority of MiniMed 780G system utilizing insulin Fiasp (insulin aspart injection) for age 7-17 will be concluded if null hypothesis is rejected.

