7.9.3.1 Primary Effectiveness Endpoint

Age 18-80:

[figure not shown]
The mean % of time, µ_{780G}, in range (TIR 70-180 mg/dL [3.9 -10.0 mmol/L]) will be estimated and compared by a non-inferiority test to the threshold of 73.7% with a margin of 7.5%^{5,6}. A significance level of 0.025 (one-sided) will be used. The 7.5%, which is approximately 100 minutes increase in TIR per day, was also observed from the HCL pivotal trials. It is loosely correlated to ~0.5% reduction in A1c as well. Analysis will be performed on the ITT and PP populations.

The hypothesis of non-inferiority is mathematically expressed as:

 H_0 : $\mu_{780G} \le 73.7\% - 7.5\%$

 H_a : $\mu_{780G} > 73.7\% - 7.5\%$

17-JUN-2024 Revision 4.0

Page 20 of 25

The null hypothesis will be tested against the alternative hypothesis using one sample t test if normality assumption is met, Wilcoxon signed rank test if normality assumption is rejected. Non inferiority of MiniMed 780G system utilizing insulin Fiasp (insulin aspart injection) for age 18-80 will be concluded if null hypothesis is rejected.

Age 7-17:

The mean % of time, μ_{780G} , in range (TIR 70-180 mg/dL [3.9 -10.0 mmol/L]) will be estimated and compared by a non-inferiority test to the threshold of 65.3% with a margin of 7.5%^{5,6}. A significance level of 0.025 (one-sided) will be used. The 7.5%, which is approximately 100 minutes increase in TIR per day, was also observed from the HCL pivotal trials. It is loosely correlated to ~0.5% reduction in A1c as well. Analysis will be performed on the ITT and PP populations.

The hypothesis of non-inferiority is mathematically expressed as:

 H_0 : μ_{780G} ≤ 65.3% − 7.5%

 H_a : $\mu_{780G} > 65.3\% - 7.5\%$

The null hypothesis will be tested against the alternative hypothesis using one sample t test if normality assumption is met, Wilcoxon signed rank test if normality assumption is rejected. Non inferiority of MiniMed 780G system utilizing insulin Fiasp (insulin aspart injection) for age 7-17 will be concluded if null hypothesis is rejected.

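### The SAP's pass/fail rule withholds the non-inferiority claim on the very result from which the SAP's primary analyses conclude non-inferiority

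*SAP*

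**What the plan says.** SAP 7.9.1 (Pass/Fail Criteria) has two bullets for each age cohort. The first ties the superiority claim to the full set of effectiveness endpoints: "Once all effective endpoints are met, the claim of superiority will be made". The second says the cohort's goal also counts as met when the primary safety and effective endpoints reach their thresholds, and ends: "However, the claim of non-inferiority will not be made".

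The sections that define the primary tests say the opposite about the same result:

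- SAP 7.9.2 (HbA1c change), adults: "Non inferiority of MiniMed 780G system utilizing insulin Fiasp (insulin aspart injection) for age 18-80 will be concluded if null hypothesis is rejected". The wording for ages 7-17 is parallel.
- SAP 7.9.3.1 (TIR), ages 7-17: "Non inferiority of MiniMed 780G system utilizing insulin Fiasp (insulin aspart injection) for age 7-17 will be concluded" on rejection of the null. The wording for adults is parallel.

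SAP 7.5.1 and 7.5.2 put these tests in a fixed order: "the procedure test hierarchically the ordered hypotheses in sequence at level" 0.025, stopping at the first non-rejection. The order is HbA1c non-inferiority, TIR non-inferiority, non-inferiority on time below 54 mg/dL, then TIR superiority.

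The pass/fail paragraph in protocol 14.5.2.1 says the study for each cohort "will be considered as success when the evaluation criteria of both primary safety and effective endpoints meets the predefined threshold per cohort", and places no bar on any claim. For HbA1c in adults, protocol 4.2.1 states: "The goal is to show non-inferiority with a margin of 0.4% comparing to a threshold of -0.5"%.

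**The concern.** Section 7.9.1 is the trial's decision rule: it says what may be claimed from each pattern of results. Read literally, its second bullet forbids the one claim that both primary tests are built to support. A cohort that meets both primaries but not the whole sequence would be a success with two endpoint-level conclusions of non-inferiority and, at the same time, an instruction not to claim non-inferiority.

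In a single-arm trial judged against fixed thresholds, prespecification of the claim carries much of the weight. As written, the sponsor would have to depart either from 7.9.1 or from 7.9.2 and 7.9.3.1 once the results are known. A correction made then would favour the sponsor and would be open to challenge.

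**Working it through.** **1. The two readings of the second bullet.** The word *primary* stands before safety but not before effective, so the bullet can be read in two ways.

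| Reading of the second bullet | Result it describes | What 7.9.1 says | What the other sections say |
|---|---|---|---|
| (a) Primary effectiveness only, as protocol 14.5.2.1 suggests | HbA1c and TIR non-inferiority nulls both rejected | Goal met, non-inferiority not claimed | 7.9.2 and 7.9.3.1 conclude non-inferiority on each |
| (b) All effectiveness endpoints | The above, plus hypoglycemia non-inferiority and TIR superiority | Bullet 1 grants superiority; bullet 2 withholds non-inferiority | Superiority on TIR implies non-inferiority on TIR |

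The implication in (b) follows from the bounds:

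- Adults: 73.7 − 7.5 = 66.2%. A mean shown to exceed 73.7% also exceeds 66.2%.
- Ages 7-17: 65.3 − 7.5 = 57.8%. A mean shown to exceed 65.3% also exceeds 57.8%.

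Both readings conflict with the rest of the SAP.

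**2. The results to which the sentence would apply.** The plan gives no figure to reproduce here. Take the commonest case for the second bullet: TIR non-inferiority met and TIR superiority not met, with the HbA1c and hypoglycemia tests taken as passed.

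Inputs:

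- One-sided alpha 0.025, from SAP 7.2: "P-values for hypothesis testing will be evaluated based on one-sided testing using significance level of 0.025".
- Thresholds and margin as above, from SAP 7.9.3.1 and 7.9.4.
- n = 100 analysed per cohort. This is an assumption; SAP 6.1 gives 100 as the minimum enrollment goal.
- SD of TIR 8 to 15 points. This is an assumption; the available text gives no SD.
- One-sample t test with 99 degrees of freedom, critical value 1.984.

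Let c = 1.984 × SD / √100. Non-inferiority is met when the observed mean exceeds bound + c, and superiority when it exceeds threshold + c. The gap between these is threshold − bound = 7.5 points for any SD or n.

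| SD | c | Adults: band of observed mean TIR | Ages 7-17: band |
|---|---|---|---|
| 8 | 1.59 | 67.8 to 75.3% | 59.4 to 66.9% |
| 15 | 2.98 | 69.2 to 76.7% | 60.8 to 68.3% |

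**3. How often a cohort lands there.** Let δ be true mean TIR minus the threshold. From the noncentral t distribution, the share of trials passing TIR non-inferiority that miss superiority is 1 − P(superiority) / P(non-inferiority):

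| δ (points) | SD 8 | SD 10 | SD 12 | SD 15 |
|---|---|---|---|---|
| 0 | 0.975 | 0.975 | 0.975 | 0.975 |
| 1 | 0.765 | 0.834 | 0.872 | 0.903 |
| 2 | 0.303 | 0.492 | 0.622 | 0.739 |
| 3 | 0.040 | 0.156 | 0.303 | 0.492 |
| 5 | 0.000 | 0.001 | 0.015 | 0.090 |

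The first row follows from the 0.025 level. At δ = 0, P(non-inferiority) is 0.9986 at SD 15 and rounds to 1.000 at the smaller SDs. The shares are the same in both cohorts because the margin is the same.

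**The case against.** The strongest defence is that *concluding* and *claiming* are different acts. Sections 7.9.2 and 7.9.3.1 govern the inference from each test. Section 7.9.1 governs what is advanced for the cohort, and since the study objective is to support labeling, *claim* could mean a labeling claim that the sponsor chooses not to make. Section 7.9.1 draws no such distinction, however. Barring the claim would also sit badly with protocol 4.2.1, which gives showing non-inferiority as the HbA1c goal. The defence does not remove the conflict.

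A second objection is that the sentence is probably a slip for *superiority*, that it restricts rather than expands what may be claimed, and that it cannot inflate type I error. All of that is fair. The hypotheses, margins, alpha and test order are unaffected, and the endpoint-level conclusions stay prespecified. But the documents do not confirm the slip, and the sentence governs the claim.

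Three narrower points stand:

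- The protocol's silence on claims is not itself a contradiction. It shows only that the SAP adds a restriction the protocol lacks.
- The frequencies rest on an assumed n and SD and on the t test, although SAP 7.2 allows a Wilcoxon signed rank test. They cover failure of TIR superiority only, not failure at the hypoglycemia step.
- Because the intent is inferred, the sponsor should confirm it when making the change.

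**Conclusion.** The concern holds. In both cohorts, the second bullet of SAP 7.9.1 contradicts SAP 7.9.2 and 7.9.3.1 on either reading, and this can be seen from the text alone. The effect is confined to the study-level claim.

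The sentence would govern a likely outcome if the system performs at or slightly above the thresholds: 97.5% of trials passing TIR non-inferiority at δ = 0 and 76 to 90% at 1 point above. It would matter much less if performance is well above them: 4 to 49% at 3 points and 0 to 9% at 5. Those shares are conditional on the assumptions stated with the calculation. They show how often the conflicting sentence would apply and do not measure any loss of power or validity. Because the sentence sits in the prespecified decision rule, it must be corrected before the data are seen.

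**What to change.** Replace the second bullet of SAP 7.9.1, once the sponsor has confirmed the intent, with:

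> If the primary safety endpoint and the primary effectiveness endpoint are met but a later endpoint in the fixed sequence is not, the goal for that cohort is met, non-inferiority to the thresholds is concluded for the primary endpoints, and the claim of superiority will not be made.

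This settles which effectiveness endpoint is meant and agrees with the fixed sequence in SAP 7.5.1 and 7.5.2 and with protocol 4.2.1 and 14.5.2.1. The non-inferiority conclusions in SAP 7.9.2 and 7.9.3.1 stay as they are.

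The cost is one sentence in a SAP revision before database lock. No protocol amendment, change in data collection or change to any test is needed.

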7.9.2 Primary Safety Endpoint

Age 18-80:

[figure not shown]
The overall mean change in HbA1c, $\Delta\mu_{780G}$, from baseline to end of 3-month study period will be estimated and compared by a non-inferiority test to the threshold of -0.50% with a margin of 0.4%⁴. A significance level of 0.025 (one-sided) will be used. Analysis will be performed on the ITT and PP populations.

The hypothesis of non-inferiority is mathematically expressed as:

 H_0 : $\Delta \mu_{780G} \ge -0.50\% + 0.4\%$

 H_a : $\Delta \mu_{780G} < -0.50\% + 0.4\%$

17-JUN-2024 Revision 4.0 Page 19 of 25

The null hypothesis will be tested against the alternative hypothesis using one sample t test if normality assumption is met, Wilcoxon signed rank test if normality assumption is rejected. Non inferiority of MiniMed 780G system utilizing insulin Fiasp (insulin aspart injection) for age 18-80 will be concluded if null hypothesis is rejected.

Age 7-17:

The overall mean change in HbA1c, $\Delta \mu_{780G}$, from baseline to end of 3-month study period will be estimated and compared by a non-inferiority test to the threshold of -0.38% with a margin of 0.4%⁴. A significance level of 0.025 (one-sided) will be used. Analysis will be performed on the ITT and PP populations.

The hypothesis of non-inferiority is mathematically expressed as:

$$H_0$$
: $\Delta \mu_{780G} \ge -0.38\% + 0.4\%$

$$H_a$$
: $\Delta \mu_{780G} < -0.38\% + 0.4\%$

The null hypothesis will be tested against the alternative hypothesis using one sample t test if normality assumption is met, Wilcoxon signed rank test if normality assumption is rejected. Non inferiority of MiniMed 780G system utilizing insulin Fiasp (insulin aspart injection) for age 7-17 will be concluded if null hypothesis is rejected.

7.9.3 Analysis of Effectiveness Endpoint

All effectiveness endpoints will be analyzed using the data from the Visit 13 to the end of the study.

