Device Deficiencies	Subject and investigational center reports of device deficiencies (DDs) will be collected on electronic Case Report Forms (eCRFs) reported by subjects and/or investigational centers for device troubleshooting and device complaints. For additional information, see Section 13 .			
Statistical Analysis for Endpoints and Hypothesis	During Study Period Safety and effectiveness endpoints will be evaluated independently for ages 18-80 and ages 7-17. Primary Safety Endpoint			
	 Age 18-80: The over to end of 3-month seinferiority with a material of 0.5% in reducing H study period. Age 7-17: The over end of 3-month stuinferiority with a material of 3-month	erall mean change in HbA study period. The goal is argin of 0.4% comparing bA1c from baseline to en all mean change in HbA1 dy period. The goal is to argin of 0.4% comparing HbA1c from baseline to e	to show non- to a threshold of - d of 3-month c from baseline to show non- to a threshold of -	
	[3.9 -10.0 mmol/L] threshold of 73.7% 7.5% and a signific • Age 7-17: The mea [3.9 -10.0 mmol/L] threshold of 65.3%	an % of time in range (T) will be estimated and co by a non-inferiority test ance level of 0.025 (one- n % of time in range (TII) will be estimated and co by a non-inferiority test ance level of 0.025 (one-	ompared to a with a margin of sided). R 70-180 mg/dL ompared to a with a margin of	
	 [3.0 mmol/L]) will be of 0.86% by a non-significance level of Age 18-80: The me [3.9 -10.0 mmol/L]] threshold of 73.7% significance level of Age 7-17: The mea [3.0 mmol/L]) will be 	an % of time in hypoglyc be estimated and compar- inferiority test with a mar- 0.025 (one-sided). an % of time in range (T) will be estimated and co by a simple superiority to 0.025 (one-sided). n % of time in hypoglyce be estimated and compar- inferiority test with a mar-	ed to a threshold rgin of 2% and a IR 70-180 mg/dL ompared to a est and a mia (< 54 mg/dL ed to a threshold	

CIP336 Clinical Investigation Plan			
D00459338	Version E	Page 29 of 159	Medtronic
	Device Deficiencies Descriptive summary will b • All reports of device		s:
Final Report	The study results will be su	ummarized and presented	in the final report.

3. Introduction

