4.2.3 Secondary Effectiveness Endpoint

- Age 18-80: The mean % of time in hypoglycemia (< 54 mg/dL [3.0 mmol/L]) will be estimated and compared to a threshold of 0.86% by a non-inferiority test with a margin of 2% and a significance level of 0.025 (one-sided).
- Age 18-80: The mean % of time in range (TIR 70-180 mg/dL [3.9 -10.0 mmol/L]) will be estimated and compared to a threshold of 73.7% by a simple superiority test and a significance level of 0.025 (one-sided).
- Age 7-17: The mean % of time in hypoglycemia (< 54 mg/dL [3.0 mmol/L]) will be estimated and compared to a threshold of 0.71% by a non-inferiority test with a margin of 2% and a significance level of 0.025 (one-sided).
- Age 7-17: The mean % of time in range (TIR 70-180 mg/dL [3.9 -10.0 mmol/L]) will be estimated and compared to a threshold of 65.3% by a simple superiority test and a significance level of 0.025 (one-sided).

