Subjects and their parents/caregivers will be trained on all parts of the device system. This training may include access to and use of digital online learning content. A training checklist for both subjects and parents/caregivers will be implemented and completed.

The completion of emergency response training, including the use of a ketone meter, will be documented for companions. Companions may be trained in person or remotely.

After completion of training on the study devices, subjects and their parents/caregivers may attend additional visits in the days immediately following the start of system use, as needed. They may also take advantage of having access to the digital learning content.

Study Period (Visits 7-15):

All subjects will use Fiasp for the remainder of the study and will continue using the study pump, with SmartGuard feature enabled (including Auto Correction), infusion set and reservoir for approximately 90 days during the study period.

Subjects should use the system with the SmartGuard feature turned on at all times with Fiasp. When prompted by the pump, subjects should take appropriate measures and follow directions on the pump to remain in or return to the SmartGuard feature. During times when subjects are not able to use the SmartGuard feature, they should use the system in Manual Mode (e.g., Suspend before low and Suspend on low).

During the first 3 weeks (between Visits 7 and 11) of the study period, a 120 mg/dL (6.7 mmol/L) Auto Basal target should be set. It is recommended that Active Insulin Time is initially set to 4 hours and then titrated towards 2-3 hours or at the investigator's discretion.

During the next 3 weeks (between Visits 11 and 13) of the study period, the Auto Basal target setting should be set to 100 mg/dL (5.5 mmol/L). Active Insulin Time is recommended to be set to 2-3 hours or at investigator's discretion.

During the remaining weeks of the study (any time after Visit 13) of the study period, the Auto Basal target as well as Active Insulin Time should be set to what is best for the individual subject, at investigator's discretion.

Note: The Auto Basal target setting and Active Insulin Time should be set as recommended above, unless there is a documented safety reason that would not permit these settings to be used.

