 - Ask subjects about adverse events and device performance
 - Review CareLink reports
 - Remind subjects about meal/exercise challenges for 120 mg/dL (6.7 mmol/L) setpoint
- Visit 9 (Phone): Day 7 (±2 days) after Visit 7
 - Adjust pump settings as needed
 - Ask subjects about adverse events and device performance
 - Review CareLink reports
 - Remind subjects about meal/exercise challenges for 120 mg/dL (6.7 mmol/L) setpoint
- Visit 10 (Phone): Day 14 (±3 days) after Visit 7
 - Adjust pump settings as needed
 - Ask subjects about adverse events and device performance
 - Review CareLink reports
 - Instruct subjects about the required meal/exercise challenges for 120 mg/dL (6.7 mmol/L) setpoint
- Visit 11 (Phone): Day 21 (±3 days) after Visit 7
 - Adjust pump settings as needed
 - \circ $\;$ Ask subjects about adverse events and device performance
 - Review CareLink reports
 - Change Auto Basal target to 100 mg/dL (5.5 mmol/L) setpoint with Active Insulin Time set to 2-3 hours or at investigator's discretion
 - Remind subjects about meal/exercise challenges for 100 mg/dL (5.5 mmol/L) setpoint
- Visit 12 (Office/Virtual Office): Day 28 (+7 days) after Visit 7
 - Ask subjects about adverse events and device performance
 - Review CareLink reports
- Visit 13 (Phone): Day 44 (±3 days) after Visit 7
 - Adjust Auto Basal target with Active Insulin Time at investigator's discretion
 - Ask subjects about adverse events and device performance
 - Review CareLink reports
 - Remind subjects about meal/exercise challenges

D00459338

•

- Review CareLink reports
- Visit 15 (Office/Virtual Office): Day 90 (+7 days) after Visit 7

Visit 14 (Office/Virtual Office): Day 60 (+7 days) after Visit 7

- Ask subjects about adverse events and device performance
- Review CareLink reports
- Return study devices
- End of Study (EOS)

Figure 4. Visit Schedule

Medtronic Business Restricted

CONFIDENTIAL 056-F275 Rev E Clinical Investigation Plan Template

CIP336 Clinical I	nvestigation Plan		
D00459338	Version E	Page 70 of 159	Mectronic

Table 5. Visit Details

		Run-In Period					S	tudy Period				
	Visit 1 (Office)	Visit 2 (Office or Virtual Office)	Visit 3* and 4* (Phone)	Visit 5 (Phone)	Visit 6 (Office or Virtual Office)	Visit 7 (Office or Virtual Office)	Visit 8* (Phone)	Visit 9, 10 & 11 (Phone)	Visit 12 (Office or Virtual Office)	Visit 13 (Phone)	Visit 14 (Office or Virtual Office)	Visit 15** (Office or Virtual Office)

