7.9.4 Analysis of Secondary Effectiveness Endpoints

Age 18-80:

Secondary Effectiveness Endpoint: The mean % time, μ_{780G}, in hypoglycemia (< 54 mg/dL [3.0 mmol/L]) will be estimated and compared by a non-inferiority test to the threshold of 0.86% with a margin of 2%⁷. A significance level of 0.025 (one-sided) will be used. Analysis will be performed on the ITT and PP populations. The 2% came from not more than 30 minutes increase in hypoglycemia per day to establish a non-inferiority test.

The hypothesis of non-inferiority is mathematically expressed as:

 H_0 : $\mu_{780G} \ge 0.86\% + 2\%$

 H_a : $\mu_{780G} < 0.86\% + 2\%$

The null hypothesis will be tested against the alternative hypothesis using one sample t test if normality assumption is met, Wilcoxon signed rank test if normality assumption is rejected. Non inferiority of

17-JUN-2024 Revision 4.0 Page 21 of 25

Form Medtronic

MiniMed 780G system utilizing insulin Fiasp (insulin aspart injection) for age 18-80 will be concluded if null hypothesis is rejected.

Secondary Effectiveness Endpoint: The mean % of time, μ_{780G} , in range (TIR 70-180 mg/dL [3.9 -10.0 mmol/L]) will be estimated and compared by a simple superiority test with a significance level of 0.025 (one-sided). Analysis will be performed on the ITT and PP populations.

The hypothesis of superiority is mathematically expressed as:

 H_0 : $\mu_{780G} \le 73.7\%$

 H_a : $\mu_{780G} > 73.7\%$

The null hypothesis will be tested against the alternative hypothesis using one sample t test if normality assumption is met, Wilcoxon signed rank test if normality assumption is rejected. Superiority of MiniMed 780G system utilizing insulin Fiasp (insulin aspart injection) for age 18-80 will be concluded if null hypothesis is rejected.

Age 7-17:

Secondary Effectiveness Endpoint: The mean % time, μ_{780G}, in hypoglycemia (< 54 mg/dL [3.0 mmol/L]) will be estimated and compared by a non-inferiority test to the threshold of 0.71% with a margin of 2%⁷. A significance level of 0.025 (one-sided) will be used. The 2% came from not more than 30 minutes increase in hypoglycemia per day to establish a non-inferiority test. Analysis will be performed on the ITT and PP populations.

The hypothesis of non-inferiority is mathematically expressed as:

 H_0 : $\mu_{780G} \ge 0.71\% + 2\%$

 H_a : $\mu_{780G} < 0.71\% + 2\%$

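### Should the superiority claim and the protocol endpoints restate the Visit 13-to-end window that the SAP sets for the effectiveness endpoints?

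*SAP*

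**What the plan says.** SAP 7.9.3 states: "All effectiveness endpoints will be analyzed using the data from the Visit 13 to the end of the study". It stands directly above the primary effectiveness endpoint (7.9.3.1) and just before the secondary effectiveness endpoints (7.9.4).

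The protocol synopsis introduces the endpoints with "During Study Period Safety and effectiveness endpoints will be evaluated independently for ages 18-80 and ages 7-17". Protocol 4.2.2, 4.2.3 and 14.5.2 give the thresholds and tests for TIR and for time below 54 mg/dL but attach no period to them. Adult TIR, for instance, is "estimated and compared to a threshold of 73.7% by a simple superiority test". HbA1c does carry its own period, from baseline to the end of the 3-month study period.

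Protocol section 5 has subjects use the pump, "infusion set and reservoir for approximately 90 days during the study period" (Visits 7 to 15). The glucose target is 120 mg/dL from Visit 7 to Visit 11 and 100 mg/dL from Visit 11 to Visit 13. Settings are then individualised: "any time after Visit 13) of the study period, the Auto Basal target as well as Active Insulin Time should be set to what" suits the subject, at the investigator's discretion. The schedule in Protocol 9.1.1 gives "Visit 13 (Phone): Day 44 (±3 days) after Visit 7" and places Visit 15 at Day 90 (+7 days).

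On conclusions, SAP 7.9.1 says "Once all effective endpoints are met, the claim of superiority will be made" and SAP 7.9.4 says "Superiority of MiniMed 780G system utilizing insulin Fiasp (insulin aspart injection) for age 18-80 will be concluded if null hypothesis is rejected". Neither sentence names a period.

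**The concern.** In a single-arm study tested against fixed thresholds, no concurrent arm shares the window, so the window itself defines what a sensor-glucose conclusion covers. Someone who reads only the protocol could take a TIR superiority claim to describe all 90 days on Fiasp, when the test uses about half of them.

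The omitted days also differ by design. They hold both fixed-target phases, four of the five study-period meal challenges, four of the five exercise challenges, and both study-period missed-bolus meals. If TIR were lower in those weeks, a superiority claim without a stated period would say more than the data tested. The study is meant to support labelling, so the scope of the claim matters.

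**Working it through.** **1. Length of the window.** Inputs are from Protocol 9.1.1.

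- Study period: Visit 15 minus Visit 7 = 90 − 0 = 90 days, which matches the stated length.
- Nominal window: 90 − 44 = 46 days; 46/90 = 51.1%. Left out: 44/90 = 48.9%.
- Shortest window: 90 − 47 = 43 days (47/90 = 52.2% left out).
- Longest window: 97 − 41 = 56 days (41/97 = 42.3% left out).

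**2. Do the texts conflict?** Days 44 to 90 lie inside Days 0 to 90. The synopsis heading, and the reference in SAP 7.2 to outcomes in the study period, both stay true when the data come from Visit 13 onward. The protocol leaves the period for TIR and time below 54 mg/dL open, and the SAP fills it.

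**3. Which tests could turn on the window?** The visible documents give no means or SDs. Assume n = 100 per cohort (the enrolment minimum), SD 8, 10 or 12 TIR points, the same SD for the window and the full period, and t(0.975, 99) = 1.984. The full-period mean is the day-weighted mean of the two phases. The shortfall in the first 44 days at which a result that passes in the window would fail over the full period is

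gap = (window mean − bound − 1.984 × SD/√100) ÷ (44/90).

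Adult superiority, bound 73.7%:

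| Window mean | SD 8 | SD 10 | SD 12 |
|---|---|---|---|
| 76% | 1.46 | 0.65 | fails in window |
| 77% | 3.50 | 2.69 | 1.88 |
| 78% | 5.55 | 4.74 | 3.93 |
| 80% | 9.64 | 8.83 | 8.02 |

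Worked case, SD 10 and mean 78%: (78 − 73.7 − 1.984)/0.4889 = 4.74. The smallest window means that pass are 75.3%, 75.7% and 76.1% for SD 8, 10 and 12. Children have the same gaps at equal distances above 65.3%.

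The reverse can also happen. At SD 10 a window mean of 75% fails, yet the full period passes if early TIR is more than (73.7 + 1.984 − 75)/0.4889 = 1.40 points higher.

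**4. The other endpoints.**

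- Primary TIR non-inferiority: its bound is 7.5 points below the superiority bound, so once superiority passes in the window, losing non-inferiority needs a gap of at least 7.5/0.4889 = 15.3 points.
- Time below 54 mg/dL, with the window mean at its threshold and a 2-point margin: (2 − 0.198)/0.4889 = 3.69 points at SD 1, and (2 − 0.397)/0.4889 = 3.28 at SD 2. The early phase would have to be that much higher.
- HbA1c: measured from baseline to the end of the study period, so the window does not touch it.

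**5. How far to trust the smallest gap.** The 0.65 arises at a window mean of 76%, only 0.3 above the 75.7% pass line. Equal phase SDs together with an equal full-period SD also imply perfect correlation between phases. With correlation ρ, the full-period SD is 10 × √((44/90)² + (46/90)² + 2ρ(44/90)(46/90)). That is 9.49 at ρ = 0.8 and 8.66 at ρ = 0.5, and the gap rises to 0.86 and 1.19.

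**The case for a change.** The strongest case for a change is that the SAP settles which analysis is run but not how its result will be described. One sentence in 7.9.3 stands against a protocol synopsis headed by the study period, a general-methods section that uses the same term, and superiority conclusions with no period. The two primary endpoints also cover different spans, and the visible text does not say so. Subjects who leave before Visit 13 have no data in the window, although the ITT set includes everyone who starts. New wording and one untested table from Visit 7 onward would need no new data.

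The facts in this stand: the window is stated once, the conclusion sentences do not repeat it, and the superiority test can turn on it. The inference does not. Section 7.9.3 covers all effectiveness endpoints, so every conclusion in 7.9.3.1 and 7.9.4 already rests on that window, and 7.9.1 is a decision rule rather than label text. The supportive table would be untested and would not gate the claim. It may also already be planned: the SAP version history records an imputation method for Visits 11 and 13 in section 7.4, SAP 7.1.4 refers to descriptive endpoints, and the sections that would hold these are not in the public text. The same withheld section may deal with early leavers. Changing the protocol would not be free either, since Protocol 16.7 requires ethics approval for a significant amendment and notification for an administrative one.

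**Conclusion.** No change follows. The SAP fills a period that the protocol leaves open, and the choice is reasonable: the fixed-target phases end at Visit 13, so the window measures the system on individualised settings. It narrows the protocol's study period without contradicting it. An analyst has one instruction to follow, and a report that describes the analysis will state the window.

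The window leaves out 42% to 52% of the study period. Under the assumed n of 100 and SDs of 8 to 12, only the last-ranked superiority test is sensitive, with tipping gaps from under 1 point near the pass line to about 8 to 10 points at a window mean of 80%. Primary non-inferiority and time below 54 mg/dL are robust under these inputs, and HbA1c is unaffected. Under Protocol 14.5.2.1, study success rests on the primary endpoints. Neither the direction nor the size of any difference between phases can be known from the documents, so no bias is shown. Restating the window in more places would repeat an existing rule and leave every test result as it is.
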